5.0 Treatment Plan

5.1 Overall Design and Plan of Study

This will be a single arm, open label phase II, single center study of maintenance therapy with daratumumab/hyaluronidase-fihj and pomalidomide post salvage ASCT in patients with multiple myeloma.

The total number of patients to be treated in this study is 56 evaluable patients.

Patients should complete 2 cycles of therapy to be evaluable. For patients who receive fewer than 2 cycles due to progressive disease will be considered evaluable. Patient who received < 2 cycles due to AEs will be inevaluable for efficacy (response). All the other analysis will be conducted using intention to treat dataset.

Patients will have standard restaging studies prior to initiation of therapy. Standard post transplant therapy per institutional guidelines will be unaltered including prophylactic antibiotics, vaccinations and restaging.

Each cycle will be defined as a 28 day cycle. Drug holidays and break in therapy including those due to holidays, physician discretion and drug delivery are allowed as needed.

5.2 Daratumumab 1800 mg/hyaluronidase-fihj 30,000 units will be given SC weekly for weeks 1-8, followed by every 2 weeks for weeks 9-24, and then every month for weeks 25 until progression. On day 1 of each cycle, doses may be held if clinically indicated (i.e., active infections) for up to 4 weeks. If longer than 4 weeks, the PI will

evaluate and determine if the patient can continue on trial or must be taken off study. After day 1 of each cycle, subsequent doses may be held/skipped if clinically indicated (i.e., active infections) per PI or treating physician's discretion.

If daratumumab administration does not commence within the specified window (Appendix A), then the dose will be considered a missed dose. Administration may resume at the next planned dosing date. A missed dose will not be made up. Any adverse event deemed to be related to daratumumab that requires a dose hold of more than 28 days will result in permanent discontinuation of daratumumab. Subjects who miss ≥ 3 consecutive planned doses of daratumumab for reasons other than toxicity will be withdrawn from treatment, unless, upon consultation with the sponsor and review of safety and efficacy, continuation is agreed upon.

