7.0 Statistical Considerations

7.1 Sample Size Justification

The primary endpoint of this study is progression-free survival (PFS). According to clinical trial [#NCT01998971 \(28\)](#), we expect that the median PFS without maintenance therapy is 12 months and the median PFS for the daratumumab-based maintenance therapy is expected to be 20 months. Given an accrual period of 36 months and a maximum follow-up time of 60 months, a sample size of 56 with the number of events of 42 will achieve the power of 0.91. The result is based on a two-sided test, a significance level of 0.05 with exponential assumption for survival time (29).

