The operating characteristics of these rules are shown in the table below.

	True Pr(Response)	True Pr (Tox)	Pr (Stop Early)	Average # treated
1	10%	15%	0.32	46.0
2	10%	33%	0.38	44.0
3	10%	40%	0.55	39.1
4	20%	25%	0.04	54.4
5	20%	33%	0.13	52.0
6	20%	40%	0.36	45.6
7	25%	20%	0.013	55.5
8	25%	33%	0.10	52.8
9	25%	40%	0.35	46.2
10	30%	20%	0.005	55.8
11	30%	33%	0.10	53.1
12	30%	45%	0.60	39.0
13	40%	20%	0.002	55.9
14	40%	33%	0.09	53.2
15	40%	45%	0.60	39.1

The dataset for efficacy will be based on evaluable patients while the dataset for safety includes all patients who receive the maintenance therapy and will be

evaluated as intention to treat (ITT). Based on the toxicity profile of daratumumab, we do not expect to have patients who receive fewer than 2 cycles due to AE's.

Patient who received < 2 cycles due to AEs will be inevaluable for efficacy (response). All the other analysis will be conducted using intention to treat dataset.

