7.3 Analysis Plan

Patients' demographic, clinical characteristics, and safety data will be summarized using descriptive statistics such as mean, standard deviation, median, interquartile range, and frequency where appropriate.

Progression-free survival is defined as the interval from the date of initiation of maintenance therapy after salvage ASCT to the earlier of the first documentation of objective disease progression or death from any cause. Disease progression will be assessed using myeloma protein measurements in serum and 24 hour urine; serum free light chain assay; bone marrow biopsy examination with MGF-based MRD testing at 6 months (+/- 2 weeks) from the start of maintenance, and then yearly as indicated; skeletal survey or other imaging as clinically indicated; and, extramedullary plasmacytoma evaluation as clinically indicated. Progression is defined by the IMWG as a 25% increase from the lowest response value in any of the following: a) serum M protein with absolute increase ≥ 0.5 g/dL, b) urine M protein with absolute increase of at least 200 mg/24 hour, c) difference between involved and uninvolved FLC levels with absolute increase of at least 10 mg/dL (in patients without measurable serum or urine M protein), d) bone marrow plasma cell percentage with absolute percentage of at least 10% (in patients without measurable serum or urine M protein or FLC levels), e) new or definite increase in size of existing bone lesions or soft tissue plasmacytoma, f) development of hypercalcemia that can be attributed solely to myeloma. Data from surviving, non-progressing patients will be censored at the last time of follow-up. Progression-free survival will be summarized descriptively using the Kaplan-Meier method (including the median, 95% confidence interval, and survival curve). The proportion of patients alive and without disease progression at 6 months of daratumumab and hyaluronidase-fihj plus pomalidomide maintenance therapy will be summarized. The estimate will be accompanied by a two-sided exact 95% binomial confidence interval. In addition, a Cox regression analysis may be performed if demographic and clinical factors potentially affecting PFS are identified.

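### The 0.91 power in 7.1 belongs to a one-sample test of median PFS against 12 months that 7.3 does not plan

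*Combined protocol and SAP*

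**What the plan says.** Section 7.1 opens with "The primary endpoint of this study is progression-free survival (PFS"). It takes a median PFS of 12 months without maintenance and expects 20 months on the study regimen. It assumes 36 months of accrual, with follow-up to at most 60 months, and concludes that "a sample size of 56 with the number of events of 42 will achieve the power of 0.91". The basis is given as "The result is based on a two-sided test, a significance level of 0.05 with exponential assumption for survival time (29"). Section 5.1 describes the design: "This will be a single arm, open label phase II, single center study of maintenance therapy".

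Section 7.3 plans three things for PFS:
- a Kaplan-Meier summary: "Progression-free survival will be summarized descriptively using the Kaplan-Meier method (including the median, 95% confidence interval, and survival curve");
- the proportion alive and progression-free at 6 months, with an exact two-sided 95% interval and no reference value;
- a Cox model on patient factors, if relevant factors are identified.

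The other tests listed in 7.3 relate safety data, prognostic factors and response to one another. The stopping rules in 7.2 use CRR and toxicity. The 12-month reference appears only in 7.1.

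The ranking of the endpoints also differs between sections. Sections 1.1 and 1.2 make CRR the primary objective and PFS the secondary one. Sections 7.1 and 7.2 call PFS primary and CRR secondary.

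**The concern.** A power figure describes a particular test. Section 7.1 fixes the reference value, target, alpha, sidedness, event count and time frame of a test, and 7.3 then does not carry that test over. Nothing names the test statistic, what triggers the analysis, or what result would count as success.

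If PFS is primary, the trial has no stated rule for its main conclusion, and the only PFS intervals that it plans have less power than the figure used to justify 56 patients. If PFS is secondary, descriptive output is reasonable, but the sample size then rests on the power of an analysis that nobody intends to perform.

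**Working it through.** **Inputs.** From 7.1: N = 56, 42 events, power 0.91, two-sided alpha 0.05, exponential survival, medians 12 and 20 months, accrual 36 months, maximum follow-up 60 months. From 5.1: single arm. Assumed: uniform accrual, no dropout (the documents give no rate), analysis 60 months after first enrolment, no early stopping under 7.2, all 56 patients analysed.

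**1. Reproduce the event count.** With λ = ln 2 / 20 = 0.03466, follow-up runs from 24 to 60 months:

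P(event) = 1 − [exp(−24λ) − exp(−60λ)] / (36λ) = 1 − (0.4353 − 0.1250) / 1.2477 = 0.7513

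56 × 0.7513 = 42.07. The plan says 42.

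**2. Reproduce the power.** For a one-sample test on the log hazard:

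Φ(√42 × ln(20/12) − 1.96) = Φ(3.311 − 1.960) = 0.912. The plan says 0.91.

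**3. Try other readings.**

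| Reading | Result |
|---|---|
| Two-arm 1:1 test, 42 events: Φ(√(42/4) × 0.5108 − 1.96) | power 0.38 |
| One-sample test, one-sided 0.05 | power 0.952 |
| Every patient followed 60 months: 56 × 0.875 = 49.0 events | power 0.947 |

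Of the readings tried, only the two-sided one-sample test against 12 months, analysed at month 60, gives both stated figures. The arithmetic in 7.1 is sound.

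**4. Power of the planned Kaplan-Meier interval, if read against 12 months.** The lower limit for the median exceeds 12 months when the lower limit for S(12) exceeds 0.5. Every patient has at least 60 − 36 = 24 months of potential follow-up. Without dropout nobody is censored before month 12, and the number progression-free at month 12 is binomial. At a true median of 20, S(12) = 0.5^(12/20) = 0.6598.

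| Limits | Needed at month 12 | Lower limit for S(12) | Power |
|---|---|---|---|
| Exact | 36/56 | 0.504 | 0.663 |
| Linear | 36/56 | 0.517 | 0.663 |
| Log-log | 36/56 | 0.503 | 0.663 |
| Log | 35/56 | 0.510 | 0.757 |

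**5. The planned 6-month proportion.** A 12-month median implies 0.5^(6/12) = 0.707 at 6 months, and a 20-month median implies 0.5^(6/20) = 0.812. The exact lower limit exceeds 0.707 at 47/56 or more, which has probability 0.377.

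**6. Power if the sized test were planned.** At 42 events it is 0.912 by the formula and 0.917 by the exact gamma test. At month 60, simulated log-hazard and one-sample log-rank tests both give about 0.92.

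**The case against.** The strongest reply is that the formal objectives make CRR primary and set out only to evaluate PFS. On that reading the output in 7.3 matches the objectives, and the fault is one passage of sizing rationale. This stands, and it is why the rating depends on which endpoint is primary. It does not remove the point, since 7.1 would still justify 56 patients by the power of an unplanned test.

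Second, 7.3 is not purely descriptive. It also plans confidence intervals and an optional model. That is correct, but no interval is tied to 12 months, and a covariate model within one arm cannot test against an external median.

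Third, the 0.66 to 0.76 assumes a use of the Kaplan-Meier interval that 7.3 does not propose. This also stands. The figures show only that the interval could not silently stand in for the sized test.

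Some stronger readings are tempting but unsupported:
- A reader might take footnote i of Appendix A, which mentions a primary analysis of PFS, as proof that PFS is the primary endpoint. The phrase can equally mean the main PFS analysis, and it does not rank endpoints. Only 7.1 does that for PFS.
- A reader might infer an inflated false-positive rate from free choice among tests and intervals. No section plans such a choice.
- A reader might infer that waiting for 42 events costs power compared with month 60. The exact gamma test at 42 events has 0.917, so it need not.
- A reader might see an unresolved analysis set for PFS, since 7.2 says "The dataset for efficacy will be based on evaluable patients". But 5.1 and 7.2 confine inevaluability to response, and 5.1 adds "All the other analysis will be conducted using intention to treat dataset". In context PFS is intention-to-treat, and the looser sentence needs at most a wording change.

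**Conclusion.** The point holds. The calculation in 7.1 is correct for a two-sided one-sample test of median PFS against 12 months, and 7.3 neither names that test nor gives a success criterion. The stated power of 0.91 therefore attaches to no planned analysis. The planned Kaplan-Meier interval, read against 12 months, would have about 0.66 (exact, linear or log-log limits) to 0.76 (log limits).

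This should be fixed, and must be fixed if PFS is confirmed as primary. The figures rest on exponential PFS, uniform accrual and no dropout. As an illustration, 10% dropout by month 12 (an assumed rate) gives about 0.89 for the one-sample tests at month 60 and 0.60 to 0.74 for the Kaplan-Meier interval, so the gap remains. Nothing here shows that 56 patients are too few, and data collection and safety are unaffected.

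**What to change.** First reconcile sections 1.1 and 1.2 with 7.1 and 7.2 on which endpoint is primary. Then make one of two changes.

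**If PFS is primary**, add to 7.3 one named one-sample test of the null hypothesis that median PFS is 12 months, at two-sided alpha 0.05, in the intention-to-treat set. State what result counts as success. The study team should state the trigger, either 42 events or a calendar date, and confirm that power for the named test at that trigger is about 0.91. Keep the Kaplan-Meier output as description.

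**If PFS is secondary and descriptive**, remove the power claim from 7.1 and state precision for a named interval method. For example: with 42 events and an estimated median of 20 months, the exponential 95% interval is 20 × exp(±1.96/√42), about 14.8 to 27.1 months.

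The cost is one or two sentences in 7.3 or a replaced statement in 7.1. No new data and no change in sample size are needed. The text should be settled before PFS results are seen.

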5.12 Duration of Treatment and Patient Participation

Patients will be informed that they have the right to withdraw from the study at any time for any reason, without prejudice to their medical care. Patients will continue indefinitely unless the following occur:

- Lack of clinical benefit
- Patient's request to withdraw from the study or refusal of further therapy
- Unacceptable toxicity
- Pregnancy
- Physicians discretion
- Disease progression.
- Completion of up to 36 Cycles of study therapy

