Note: Study drug is defined as daratumumab and pomalidomide.																			
a) To occur within 7 days after discontinuation of all study treatment.																			
b) In the 90 (+3) days after the last dose of daratumumab for safety follow-up visits. For subjects who discontinue study treatment before PD, disease evaluations should continue to be performed at the frequency specified below until confirmed PD, death, start of a new anticancer treatment, withdrawal of consent to study participation, or end of the study, whichever occurs first. Once PD is confirmed, subsequent disease evaluation time points are not required.																			
- Every 8-12 weeks (± 3 days), at clinician's discretion: SPEP and 24-hour UPEP assessments, and serum calcium corrected for albumin																			
- Every 4 weeks (± 3 days), or at clinician's discretion: physical examination of extramedullary plasmacytomas if applicable																			
- Every 12 weeks (± 14 days), or at clinician's discretion: radiologic imaging of extramedullary plasmacytomas if applicable																			
- When CR is suspected or maintained: serum FLC, serum and urine immunofixation																			
- As clinically indicated: skeletal survey																			

- Evidence of clinical relapse will also be documented at the time at which it is first detected.

After PD is determined, patient will be taken off study and no further study evaluations will be needed.

- c) Blood pressure is to be measured at the following time points on Cycle 1 Days 1: immediately pre-administration, at the end of administration, 30 minutes post administration, 60 minutes post administration, and then hourly until 6 hours post administration. On Cycle 1 Day 8: immediately pre-administration, at the end of administration, 30 minutes post administration, 60 minutes post administration, and 120 minutes post administration. On Cycle 1 Day 15 onward: immediately pre-administration, at the end of administration, 15 minutes post administration. Infusion observation times and vital signs may be adjusted per PI discretion.
- d) Pre-infusion medications to be given before all daratumumab infusions (if necessary, oral pre-infusion medications may be administered at the subject's home on the day of the infusion, provided they are given within 3 hours prior to the infusion)
- e) Unless otherwise stated, all blood and urine samples must be obtained before administration of study treatment.

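### The 6-month progression-free proportion has an exact binomial interval but no rule for patients censored before month 6; the month-6 Kaplan-Meier estimate should be reported instead

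*Combined protocol and SAP*

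**What the plan says.** Section 7.3 measures PFS from the start of maintenance to progression or death and sets the censoring rule: "Data from surviving, non-progressing patients will be censored at the last time of follow-up". The main summary follows: "Progression-free survival will be summarized descriptively using the Kaplan-Meier method (including the median, 95% confidence interval, and survival curve"). A month-6 Kaplan-Meier estimate is not among the listed outputs.

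The same paragraph then adds a second summary of the same endpoint: "The proportion of patients alive and without disease progression at 6 months of daratumumab and hyaluronidase-fihj plus pomalidomide maintenance therapy will be summarized". Its precision statement is: "The estimate will be accompanied by a two-sided exact 95% binomial confidence interval". Nothing there or elsewhere says how a patient censored before month 6 is counted.

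Three other places bear on this:

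- Section 7.2, on analyses other than response: "All the other analysis will be conducted using intention to treat dataset". This presumably keeps early-censored patients in the denominator but does not settle the numerator.
- Section 5.12 lists among the reasons for ending participation: "Patient's request to withdraw from the study or refusal of further therapy".
- Appendix A, footnote b, continues disease evaluation for patients who stop treatment before progression, "until confirmed PD, death, start of a new anticancer treatment, withdrawal of consent to study participation, or end of the study, whichever occurs first".

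**The concern.** A binomial proportion treats each patient's month-6 status as observed. A patient who withdraws consent at month 3, or starts another myeloma therapy at month 4 and leaves scheduled disease evaluation, has no observed status at month 6. The analyst must then count that patient as a failure, count them as progression-free, or drop them. The plan makes no choice, so it could be made after the data are seen.

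At stake is a reported 6-month PFS rate and interval that depend on an unstated convention and may disagree with the month-6 point of the trial's own Kaplan-Meier curve. For scale, the two medians in Section 7.1 imply 6-month PFS of 70.7% (12 months) and 81.2% (20 months), a gap of 10.5 points.

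**Working it through.** **Inputs from the documents.** N = 56, 42 events, medians of 12 and 20 months, exponential PFS, two-sided 0.05, 36 months' accrual and 60 months' maximum follow-up (all Section 7.1). **Assumed:** the probability c of being censored by month 6, varied over 0, 5, 10 and 20% because the documents give no dropout rate; exponential censoring, independent of progression unless stated.

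**1. The plan's own figures.** The plan gives no figure for the 6-month proportion, so the design figures were checked first.

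- Power = Φ(√42 × ln(20/12) − 1.96) = Φ(3.311 − 1.960) = 0.912, against 0.91 stated.
- With λ = ln 2/20 = 0.03466 per month and uniform accrual, expected events = 56 × [1 − (e^(−24λ) − e^(−60λ))/(36λ)] = 56 × 0.7513 = 42.07, against 42 stated.

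Both reproduce when 60 months is total study time; adding 60 months after accrual would give 52.0 events. Each patient therefore has at least 60 − 36 = 24 months of planned follow-up. Administrative censoring before month 6 does not arise at the final analysis, and only withdrawal, loss to follow-up or new therapy matters.

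**2. True 6-month PFS.** S(6) = e^(−6λ) = 0.8123 for a 20-month median and 0.7071 for a 12-month median. With complete data, 45/56 = 80.4%, exact 95% interval 67.6% to 89.8%.

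**3. The three conventions at c = 10%.** The censoring rate is μ = −ln(0.9)/6 = 0.01756 per month.

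- Seen progression-free at month 6: S(6) × (1 − c) = 0.8123 × 0.9 = 0.731.
- Censored before month 6 and before any event: q = μ/(λ + μ) × (1 − 0.731) = (0.01756/0.05222) × 0.269 = 0.0905, or 56 × 0.0905 = 5.07 patients.
- Counted as failures: 0.731.
- Counted as progression-free: 0.731 + 0.0905 = 0.8215.
- Excluded: 0.731/(1 − 0.0905) = 0.804.

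**4. Simulation.** There were 20,000 trials of 56 patients per setting, with a 20-month median and truth 0.8123. Each cell gives the mean estimate, with coverage of the nominal 95% interval in brackets. Intervals are exact binomial for the first three conventions and log-log for Kaplan-Meier.

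| Censored by month 6 (assumed) | Mean number censored | Failures | Progression-free | Excluded | Kaplan-Meier |
|---|---|---|---|---|---|
| 0% | 0 | 0.8123 (0.962) | 0.8123 (0.962) | 0.8123 (0.962) | 0.8123 (0.962) |
| 5% | 2.56 | 0.7713 (0.878) | 0.8170 (0.964) | 0.8083 (0.965) | 0.8124 (0.951) |
| 10% | 5.07 | 0.7313 (0.679) | 0.8219 (0.962) | 0.8041 (0.963) | 0.8127 (0.952) |
| 20% | 10.13 | 0.6505 (0.195) | 0.8315 (0.960) | 0.7943 (0.957) | 0.8127 (0.956) |

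Over 5% to 20% the bias in points is −4.1 to −16.2 (failures), +0.5 to +1.9 (progression-free), −0.4 to −1.8 (excluded), and below 0.1 for Kaplan-Meier. With a 12-month median and 20% censored, the failure, progression-free and excluded conventions average 0.566, 0.736 and 0.682 against 0.707, that is −14.1, +2.9 and −2.5 points.

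**5. Informative censoring.** The independence assumption was then dropped by letting the progression hazard rise four-fold after dropout (an assumed value). With 10% censored, the truth was 0.791, Kaplan-Meier 0.813 and the excluded convention 0.804. With 5%, they were 0.802, 0.812 and 0.808.

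**The case against.** The strongest reply is that the large error arises only under a convention the plan never adopts. A reader might infer from the failure column that the reported rate will be about 8 points too low, with 68% coverage. The documents do not support that: they neither count censored patients as failures nor give a dropout rate. Under the other two conventions at 10% censoring the shift is about 1 point, coverage is nominal, and the interval itself is about 22 points wide. This stands, and it limits the severity.

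Second, the affected group may be small. Refusing further therapy is not loss of PFS follow-up, since footnote b of Appendix A continues disease evaluation off treatment. This also stands. It narrows the group without emptying it, because the same footnote ends evaluation at consent withdrawal or new therapy.

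Third, a reader might infer that Kaplan-Meier removes the bias. It does so only if censoring is independent of progression. Section 5.12 includes lack of benefit and physician discretion among the reasons to stop, and a switch of therapy may well carry information about progression. In the informative setting above, Kaplan-Meier was further from the truth than the excluded proportion.

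Fourth, the curve is already planned, so its month-6 value will be visible, and nothing is decided on the proportion. Both are true. They do not tell the analyst which 6-month figure to report or how to count the early-censored patients.

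**Conclusion.** The point holds as a low-severity improvement. Section 7.3 summarises one endpoint in two ways, and the binomial one lacks a rule for patients censored before month 6. Its possible size runs from nothing, with no early censoring, to about −16 points if 20% are censored and counted as failures. Under the planned 20-month median the other two conventions stay within about 2 points. These sizes rest on assumed censoring rates and exponential PFS.

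It would go too far to say that the exact interval is unusable or that the 6-month result will be wrong. With complete month-6 status it is valid and its estimate equals the Kaplan-Meier one. Section 7.1 sizes the trial on medians and Section 7.2 stops it on remission and toxicity, so no power figure or stopping rule is affected.

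**What to change.** In Section 7.3, report 6-month PFS as the Kaplan-Meier estimate at month 6 on the ITT set, with a log-log (Greenwood) 95% confidence interval, and state that it assumes censoring independent of progression. List the number censored before month 6, with reasons, beside it.

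If the binomial proportion is kept, label it a sensitivity analysis and pre-specify its denominator and how patients censored before month 6 count. Showing it both with those patients as failures and as progression-free would bracket the result without relying on independence.

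The cost is one or two sentences. No extra patients, visits or data are needed, and the curve is already planned.
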